2.4 Study Design

For clinicaltrials.gov and Stanford Clinical Trials Directory compliance

- State the primary purpose for the protocol:
 - **Supportive Care:** protocol designed to evaluate one or more interventions where the primary intent is to maximize comfort, minimize side effects or mitigate against a decline in the subject's health or function. In general, supportive care interventions are not intended to cure a disease.
- State the interventional model:
 - **Parallel:** one of two groups in parallel for duration of study.
- State the number of intervention arms:
 - **Two intervention arms.**
- State whether the study will be masked:
 - **Double Blind:** both parties unaware of intervention assignment
- State whether the study is randomized: **Yes.**

- State type of primary outcome or outcome that the protocol is designed to evaluate: **Efficacy**

2.5 Correlative Studies Background

There are no planned correlative studies.

3. PARTICIPANT SELECTION AND ENROLLMENT PROCEDURES

Refer to the Participant Eligibility Checklist in Appendix A.

3.1 Inclusion Criteria

- 3.1.1 Prior diagnosis or presumed diagnosis of breast cancer or undergoing prophylactic treatment.
- 3.1.2 Greater than 18 years old.
- 3.1.3 Female.
- 3.1.4 Undergoing microsurgical breast reconstruction with abdominal free flap.
- 3.1.5 Ability to understand and the willingness to sign a written informed consent document.

3.2 Exclusion Criteria.

- 3.2.1 True allergy to local anesthetics or opioids.
- 3.2.2 History of addiction to narcotics within the last 24 months
- 3.2.3 History of chronic pain on opioids within the last 24 months.
- 3.2.4 Specific mental health issues such as schizophrenia or bipolar disorder.
- 3.2.5 Patients who are pregnant.

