4.2 Hospitalization for reconstructive surgery

4.2.1 TAP Catheter Placement and Dosing:

On the day of surgery, bilateral TAP catheters will be placed using ultrasound guidance by the anesthesiologist in the pre-operative staging area prior to entering the operating room. Patients in the experimental group will receive an infusion of 0.125% bupivacaine and patients in the control group will receive an infusion of saline. Both groups will receive the following dosing:

- Initial bolus of 15mL pre-operatively
- 10mL bolus q4h intraoperatively with an option of 1-2mL per hour basal rate
- 10mL bolus q4h post-operatively with an option of 1-2mL per hour basal rate

TAP catheters will be discontinued on post-operative day (POD) 2, and the time will be recorded.

4.2.2 Post-Operative Pain Medication Regimen:

All patients will be provided with a patient controlled analgesia (PCA) infusion post-operatively providing IV hydromorphone. The PCA will be discontinued on POD2. Other pain medications available immediately after leaving the operating room will include the following:

- Acetaminophen IV or PO around the clock, per physician preference
- IV hydromorphone (dilaudid) 0.5 mg every 4 hours as needed for breakthrough pain, with an option to titrate up dose or frequency, per physician preference
- PO oxycodone 5-10 mg every 3 hours as needed for pain, with an option to titrate up dose or frequency, per physician preference
- Any pre-operative medications may be continued

4.2.3 Post-Operative Anti-Emetic Medication Regimen:

All patients will have available IV ondansetron (zofran) 4 mg every 4 hours as needed for nausea. Patients unable to take ondansetron will be given metocloprmiade (reglan).

4.2.4 Post-Operative Measurements:

Patients will be asked to rate their pain level on the Visual Analog Scale (VAS) every 4 hours while hospitalized unless they are sleeping. The total dosage of IV hydromorphone administered (via both the PCA and the as needed medications for breakthrough pain) will be recorded in 8-hour periods (midnight to 8am, 8am to 4pm, 4pm to midnight). The use of other pain medications, as well as anti-emetic medications, will be recorded in the same 8-hour periods. Time to ambulation, time to first bowel movement after surgery, and time to discharge will be recorded.

4.2.5 Evaluation for Discharge:

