10.1 Primary Outcome Measure: Post-operative Narcotic Usage

10.1.1 Measurement Definition

Post-operative Narcotic Usage will be measured in total oral morphine equivalents (OME) calculated by summing all narcotics used in the first 48 hours post-operatively.

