10.1.2 Measurement Methods

Post-operative Narcotic Usage will be measured by review the patient's chart and medication administration history and totaling all narcotics administered.

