12.4.2. Analysis Plan

Differences between the two arms will be evaluated using an analysis of covariance model. The comparison of the two arms will be made adjusting for the variables used in the stratified randomization. The primary analysis will be a modified intent-to-treat principle (using recorded values where available regardless of compliance).

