APPENDIX A: Participant Eligibility Checklist

Protocol Title:	A Randomized Double-blinded, Placebo-Controlled Trial: Use of Transversus Abdominis Plane (TAP) Block in Breast Cancer Patients Undergoing Microsurgical Breast Reconstruction with Abdominal Free Flap
Protocol Number:	34315
Principal Investigator:	[name], FACS

II. Subject Information:

Subject Name/ID:
Gender:  Male  Female

III. Study Information:

SRC Approved IRB Approved Contract signed

IV. Inclusion/Exclusion Criteria

Inclusion Criteria (From IRB approved protocol)	Yes	No	Supporting Documentation*
1. Female			
2. Greater than 18 years old			
3. Undergoing microsurgical breast reconstruction with abdominal free flap			
4. Has a prior diagnosis or presumed diagnosis of breast cancer or undergoing prophylactic treatment			
5. Capable of providing informed consent			
Exclusion Criteria (From IRB approved protocol)			
1. Allergic to local anesthetics or opioids			
2. History of addiction to narcotics within last 24 months			
3. History of chronic pain on opioids within last 24 months			
4. Specific mental health issues such as schizophrenia or bipolar disorder			
5. Pregnant			

*All subject files must include supporting documentation to confirm subject eligibility. The method of confirmation can include, but is not limited to, laboratory test results,

radiology test results, subject self-report, and medical record review.

IV. Statement of Eligibility

By signing this form of this trial I verify that this subject is [**eligible** / **ineligible**] for participation in the study. This study is approved by the Stanford Cancer Institute Scientific Review Committee, the Stanford IRB, and has finalized financial and contractual agreements as required by Stanford School of Medicine's Research Management Group.

Treating Physician Signature:	Date:
Printed Name:	

Secondary Reviewer Signature:	Date:
Printed Name:	

Study Coordinator Signature:	Date:
Printed Name:

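### Opioid use at the time of surgery is neither recorded as a baseline value nor adjusted for, so any continued home opioid adds avoidable variance to the 48-hour primary outcome

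*Combined protocol and SAP*

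**What the plan says.** **Eligibility.** Three exclusions in section 3.2 mention opioids: "True allergy to local anesthetics or opioids", "History of addiction to narcotics within the last 24 months" and "History of chronic pain on opioids within the last 24 months". The Appendix A checklist has the same scope, for example "History of chronic pain on opioids within last 24 months". None asks whether the patient is taking an opioid when she comes to surgery.

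**Home medication.** Among the post-operative pain provisions, section 4.2.2 states: "Any pre-operative medications may be continued". Opioids are not excepted.

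**Primary outcome.** Section 10.1.1 defines post-operative narcotic usage in OME, "calculated by summing all narcotics used in the first 48 hours post-operatively". Section 10.1.2 obtains it from the chart and medication administration history by "totaling all narcotics administered". Neither section separates or subtracts a home dose.

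**Adjustment.** Section 12.4.2 specifies an ANCOVA: "The comparison of the two arms will be made adjusting for the variables used in the stratified randomization". Sections 3.4 and 12.1.1 show one such variable, unilateral or bilateral reconstruction.

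**Baseline data.** The study calendar (section 9) lists medical history and a pain evaluation at the Pre-Study visit. It does not list a pre-operative opioid dose.

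**The concern.** The primary outcome is meant to reflect opioid need after surgery, which the block may change. The exclusions work by diagnosis, not by current use. A patient taking opioids short-term for an acute problem or after an earlier operation meets none of them. She may continue her opioid, and whatever is given in the first 48 hours counts towards her total.

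That part of the total has nothing to do with the treatment arm. It widens the spread of an outcome planned with an SD of 20 mg and a target difference of 10 mg. The scale is tight: 5 mg OME/day carried over for 48 hours is 10 mg, as large for that patient as the whole target difference. Because no baseline dose is called for, the analysis has no prespecified way to remove this variance.

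**Working it through.** **1. Inputs.** From section 12.6: SD 20 mg, difference 10 mg, two-tailed t-test, power 80%, 64 per arm. Alpha is not stated; 0.05 two-sided is assumed.

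**2. The plan's own figure.** With a standardised difference of 10/20 = 0.5, the two-sample t-test needs 63.77 per arm, rounded up to 64. Power at 64 per arm is 80.1%. The plan's figure reproduces. A one-sided test would need about 51, so the two-sided 0.05 reading is the one that fits.

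**3. Model for continued home opioids.** Suppose a share p of patients, independent of arm, adds a fixed amount h to the 48-hour total, and everyone otherwise has SD 20. Then

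SD_new = sqrt(20² + p(1 − p)h²), with h = 2 × daily home dose.

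The documents give neither p nor h. The illustration takes 2 or 4 such patients of 128 (p = 1.6% or 3.1%) and home doses from 5 to 60 mg OME/day.

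**4. One case in full.** At 30 mg/day, h = 60. With 2 of 128, p(1 − p) = 0.01538, so the added variance is 0.01538 × 3600 = 55.4, and SD_new = sqrt(455.4) = 21.3. The t-test with difference 10 and 64 per arm then has power 74.9%.

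**5. Range.**

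| Home dose (mg OME/day) | h over 48 h (mg) | SD, 2 of 128 | Power | SD, 4 of 128 | Power |
|---|---|---|---|---|---|
| 5 | 10 | 20.0 | 80.0% | 20.1 | 79.9% |
| 10 | 20 | 20.2 | 79.5% | 20.3 | 79.0% |
| 20 | 40 | 20.6 | 77.8% | 21.2 | 75.5% |
| 30 | 60 | 21.3 | 74.9% | 22.6 | 70.1% |
| 60 | 120 | 24.9 | 61.5% | 28.9 | 49.3% |

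A simulation that kept the non-normal mixture, run for the 30 and 60 mg/day rows, agreed to within 1 percentage point.

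**6. Effect on an arm mean.** One such patient moves a 64-patient mean by h/64: 0.94 mg at h = 60 and 1.88 mg at h = 120. The standard error of the arm difference at SD 20 is 20 × sqrt(2/64) = 3.54 mg, so these shifts are 0.27 and 0.53 standard errors. They are the same random variation that already enters SD_new, not a second loss to add to the power loss.

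**The case against.** **The main high-dose groups are already out.** Addiction and chronic pain on opioids are both excluded with a 24-month look-back, so only a residual group is left. This stands, and it makes the upper rows of the table harder to reach.

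**Who is in the residual group is partly inference.** A reader might infer that a patient on maintenance opioid treatment for an older addiction clearly passes the checklist. Section 3.2.2 does not say when an addiction under current treatment counts as ended, and an investigator could well apply the exclusion. A reader might also infer that the trial expressly admits delayed reconstruction in patients still taking opioids after mastectomy. Section 3.1 sets no limit on timing, but no eligibility item says this, and nothing states that such patients take opioids at surgery. The point needs neither example, because the criteria do not address current use at all.

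**Full addition is an upper case.** Section 4.2.2 offers every patient PCA hydromorphone, further IV hydromorphone and oral oxycodone. A home opioid might partly replace these, and continuing it is permitted, not required. This stands: the power figures assume no substitution.

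**The SD may already include such patients.** Section 12.6.2 gives no source for 20 mg. If it came from comparable unselected patients, the loss is already in the plan's power. This also stands.

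**The dose may be captured on forms not shown.** The case report forms are not in the documents, so a field could exist. The stated covariates would still leave it unused in the primary analysis.

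**Conclusion.** The gap is real: other opioid use at surgery is not excluded, may continue, counts in the primary outcome and is not adjusted for. The harm is lost precision of unknown size. For 2 to 4 affected patients it runs from negligible at 5-10 mg OME/day, through a few points of power at 20 mg/day and 5 to 10 points at 30 mg/day, to a severe loss at 60 mg/day. These figures rest on assumed shares and doses, full addition of the home dose, a two-sided alpha of 0.05, and an SD of 20 mg that describes patients without home opioids.

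Two stronger readings are not supported. A reader might infer that home opioids bias the comparison. They do not do so systematically, because allocation is randomised and home use precedes it; a chance imbalance is noise already reflected in the SD. A reader might also infer that the trial is underpowered for this reason. The documents give no share or dose from which that could be concluded.

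The point is a cheap improvement, not a flaw that threatens the trial's validity.

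**What to change.** 1. Add to the Pre-Study column of the study calendar, alongside medical history, the pre-operative daily opioid use in OME/day. Count scheduled and as-needed use, and enter zero where there is none.
2. In section 12.4.2, name this value as a prespecified covariate beside laterality in the primary ANCOVA.
3. In section 10.1.1, state explicitly whether continued home opioids count in the 48-hour total, so that the outcome and the covariate are read together.

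The cost is one case report form field and one degree of freedom. No patient is lost and no treatment changes. If few patients use opioids, or their doses are low, the gain will be small, but the record will then show that.

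An added exclusion is a different trade-off. It would narrow eligibility, and one limited to regularly scheduled opioids would still admit as-needed users. Whether to change eligibility or the continuation of home medication is for the clinical team.

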3.3 Informed Consent Process

All participants must be provided a consent form describing the study with sufficient information for participants to make an informed decision regarding their participation. Participants must sign the IRB approved informed consent prior to participation in any study specific procedure. The participant must receive a copy of the signed and dated consent document. The original signed copy of the consent document must be retained in the medical record or research file.

3.4 Randomization Procedures

Patients will be randomized within their surgery subtype (unilateral or bilateral) by the Stanford

Pharmacy to receive TAP catheters infusing either bupivacaine or saline. Randomization will occur using a computer software program to be implemented by the Pharmacy. The anesthetist placing the block, the surgeon performing the surgery, the nurses caring for the patient while hospitalized, and the research coordinators collecting data will be blinded to the randomization status.

3.5 Study Timeline

Primary Completion:

The study will reach primary completion approximately 48 months from the time the study opens to accrual.

Study Completion:

The study will reach study completion approximately 52 months from the time the study opens to accrual.

4. TREATMENT PLAN

4.1 Pre-operative clinic visit

4.1.1 All patients undergoing microsurgical breast reconstruction for breast cancer with abdominal free flap are screened for enrollment.

4.1.2 Patients meeting inclusion criteria and not meeting exclusion criteria are enrolled. (See Appendix A for further details on inclusion and exclusion criteria.)

4.1.3 Consent forms for study enrollment are signed.

4.1.4 BREAST-Q¹⁹ questionnaire filled out.

4.2 Hospitalization for reconstructive surgery

4.2.1 TAP Catheter Placement and Dosing:

On the day of surgery, bilateral TAP catheters will be placed using ultrasound guidance by the anesthesiologist in the pre-operative staging area prior to entering the operating room. Patients in the experimental group will receive an infusion of 0.125% bupivacaine and patients in the control group will receive an infusion of saline. Both groups will receive the following dosing:

- Initial bolus of 15mL pre-operatively
- 10mL bolus q4h intraoperatively with an option of 1-2mL per hour basal rate
- 10mL bolus q4h post-operatively with an option of 1-2mL per hour basal rate

TAP catheters will be discontinued on post-operative day (POD) 2, and the time will be recorded.

4.2.2 Post-Operative Pain Medication Regimen:

All patients will be provided with a patient controlled analgesia (PCA) infusion post-operatively providing IV hydromorphone. The PCA will be discontinued on POD2. Other pain medications available immediately after leaving the operating room will include the following:

- Acetaminophen IV or PO around the clock, per physician preference
- IV hydromorphone (dilaudid) 0.5 mg every 4 hours as needed for breakthrough pain, with an option to titrate up dose or frequency, per physician preference
- PO oxycodone 5-10 mg every 3 hours as needed for pain, with an option to titrate up dose or frequency, per physician preference
- Any pre-operative medications may be continued

4.2.3 Post-Operative Anti-Emetic Medication Regimen:

All patients will have available IV ondansetron (zofran) 4 mg every 4 hours as needed for nausea. Patients unable to take ondansetron will be given metocloprmiade (reglan).

4.2.4 Post-Operative Measurements:

Patients will be asked to rate their pain level on the Visual Analog Scale (VAS) every 4 hours while hospitalized unless they are sleeping. The total dosage of IV hydromorphone administered (via both the PCA and the as needed medications for breakthrough pain) will be recorded in 8-hour periods (midnight to 8am, 8am to 4pm, 4pm to midnight). The use of other pain medications, as well as anti-emetic medications, will be recorded in the same 8-hour periods. Time to ambulation, time to first bowel movement after surgery, and time to discharge will be recorded.

4.2.5 Evaluation for Discharge:

Patients will be evaluated daily for meeting discharge criteria as per normal Institution guidelines that are standard of care for patients undergoing flap-based breast reconstruction. That is, discharge criteria for patients on this study are the same as Institutional discharge criteria.

4.3 Post-operative follow-up (1-6 months post-operatively)

4.3.1 The post-operative BREAST-Q questionnaire¹⁹ will be administered at a clinic visit 1-6 months after surgery. If the study subject is unable to attend clinic in person during this time period, they will be asked to return the post-operative BREAST-Q questionnaire via email or fax. If the study subject does not return the post-operative BREAST-Q survey after 3 attempts by phone or email, the subject will be considered lost to follow-up and no further attempts will be made to have the patient complete the questionnaire.

4.4 General Concomitant Medication and Supportive Care Guidelines

Please refer to Section 4.2 above for details on concomitant medications.

4.5 Criteria for Removal from Study

Patients will be removed from the study if the study proves harmful to patient's health, if there is recurrence of cancer during study enrollment, if the patient withdraws consent at any time, and/or if the study protocol director deems it necessary to remove the patient from the study for any reason.

4.6 Alternatives

Sterile surgical technique and precautions will be utilized for placement of each TAP catheter. Alternative treatments for patients will include all pain medications offered for post-operative pain (detailed in Section 4.2).

5. INVESTIGATIONAL AGENT/DEVICE/PROCEDURE INFORMATION

5.1 Investigational Agent/Device/Procedure

5.1.1 Nimbus Ambulatory Infusion System

Product Description:

- Adjustable volume to be infused (VTBI), variable basal rate and bolus delivery

[figure not shown]
Protocol for RCT of TAP Blocks in Breast Reconstruction

- Single patient use.
- Basal rate 0 – 14 mL/hr. Rate may be titrated during therapy delivery
- Optional keypad lockout function
- Kit comes with a pump, fanny pack, 10-day lithium ion battery, Clinician Guide and Patient Quick Reference Guide

Nimbus Infusion Pump IV Administration Set:

Product Description:

- 1 Each 67" (170cm) Long
- Priming Volume: 3mL (approx.)
- Fluid path is sterile, non-Pyrogenic
- One bag spike (1)
- One Cassette (3)
- One 1.2 Micron, air-eliminating Filter (4) One Slide Clamp (5)
- One Male Luer Lock Adaptor (6)

The Nimbus Ambulatory Infusion System is intended to deliver medications and/or fluids to a patient under the direction or supervision of a physician or other certified healthcare provider. The device is indicated for subcutaneous, epidural, perineural, and intravenous infusion. For the purposes of the Implementation, the Nimbus Ambulatory Infusion System will be customized to the Institution protocol presently:

- Deliver a 15 mL bolus to establish the primary block
- Deliver a 10 mL auto-bolus every four hours intraoperatively, with the option for
- a 1 or 2 mL per hour basal rate
- Deliver a 10 mL per hour auto-bolus post-operatively, with the option for a 1 or 2 mL per hour basal rate

The Nimbus Ambulatory Infusion System is capable of carrying:

- Time stamped infusion parameters
- Incidences of bolus requests vs. bolus delivered

to provide Institution with access to infusion history data and patient interactions as a uniquely designed data carrier device.

The Nimbus Ambulatory Infusion System is intended to be used in an environment where patient care is provided by Healthcare Professionals, i.e. Physicians, Nurses, and Technicians, who will determine when use of the device is indicated, based upon their professional assessment of the

patient's medical condition.

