6. DOSE MODIFICATIONS

Doses will be standardized across each patient group to the following, and no modifications shall be made:

- Initial bolus of 15mL pre-operatively
- 10mL bolus q4h intraoperatively with an option for 1-2mL per hour basal rate
- 10mL bolus q4h post-operatively with an option for 1-2mL per hour basal rate

The Intervention group will receive an infusion of 0.125% bupivacaine, while the Control/Placebo group will receive an infusion of normal saline.

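### The pump set-up list in Section 5.1.1 gives an hourly 10 mL post-operative bolus, where Sections 4.2.1 and 6 prescribe it every four hours

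*Combined protocol and SAP*

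**What the plan says.** Section 5.1.1 describes the device and says that "the Nimbus Ambulatory Infusion System will be customized to the Institution protocol presently". It then lists the settings. The intra-operative line begins "Deliver a 10 mL auto-bolus every four hours intraoperatively, with the option for" and goes on to a basal rate of 1 or 2 mL per hour. The post-operative line is "Deliver a 10 mL per hour auto-bolus post-operatively, with the option for a 1 or 2 mL per hour basal rate".

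Section 4.2.1 is the treatment plan. It states "Both groups will receive the following dosing" and gives the post-operative item as "10mL bolus q4h post-operatively with an option of 1-2mL per hour basal rate". It also fixes the drug: "Patients in the experimental group will receive an infusion of 0.125% bupivacaine", with saline for controls, through catheters placed on both sides.

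Section 6 opens with "Doses will be standardized across each patient group to the following, and no modifications shall be made" and repeats "10mL bolus q4h post-operatively with an option for 1-2mL per hour basal rate". The abbreviation list defines Q4H as every 4 hours.

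**The concern.** The same document gives two post-operative bolus intervals, one hour and four hours, for the same 10 mL volume. The hourly figure cannot be a loose description of the background infusion, because the same line gives the basal rate separately.

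What is at stake is treatment delivery and patient safety. Someone who programs the pump from 5.1.1 alone would see nothing to signal a problem. The bolus volume would be four times that prescribed in both arms, and in the active arm so would the bolus dose of bupivacaine. Section 7.1 links the main acute reactions to dose and high plasma levels, and Section 5.1.3 gives a half-life of 2.7 hours, so hourly boluses would fall well inside one half-life. A pump run this way would also depart from the fixed dosing in Section 6.

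**Working it through.** The bolus interval is a prescribed setting, so no formula reproduces it. The check is a comparison of the sections, followed by dose arithmetic.

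**Comparison**

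| Setting | 5.1.1 | 4.2.1 | 6 |
|---|---|---|---|
| Initial bolus | 15 mL | 15 mL | 15 mL |
| Intra-operative bolus | 10 mL every 4 h | 10 mL every 4 h | 10 mL every 4 h |
| Post-operative bolus | **10 mL every 1 h** | 10 mL every 4 h | 10 mL every 4 h |
| Optional basal rate | 1 or 2 mL/h | 1–2 mL/h | 1–2 mL/h |

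Everything agrees except the post-operative interval in 5.1.1.

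**Inputs**
- Bolus 10 mL (all three sections).
- Basal rate 0, 1 or 2 mL/h, since it is optional.
- Concentration 0.125% (4.2.1 and 6), that is 1.25 mg/mL.
- Two catheters (4.2.1). Whether volumes are per catheter or totals is not stated, so both are shown.
- The pre-operative 15 mL bolus is left out because it falls before the post-operative period.

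**Formulas**
- mL per 24 h = number of boluses × 10 + 24 × basal rate
- mg per 24 h = mL × 1.25, doubled if volumes are per catheter

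Every four hours means 6 boluses per 24 h; hourly means 24.

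| Basal (mL/h) | Every 4 h: mL | Hourly: mL | Every 4 h: mg, totals | Hourly: mg, totals | Ratio | Every 4 h: mg, per catheter | Hourly: mg, per catheter |
|---|---|---|---|---|---|---|---|
| 0 | 60 | 240 | 75 | 300 | 240/60 = 4.00 | 150 | 600 |
| 1 | 84 | 264 | 105 | 330 | 264/84 = 3.14 | 210 | 660 |
| 2 | 108 | 288 | 135 | 360 | 288/108 = 2.67 | 270 | 720 |

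The mL columns are the volumes as programmed, before any doubling.

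**Excess.** The volume difference is the same at each basal rate: 240 − 60 = 264 − 84 = 288 − 108 = 180 mL. At 1.25 mg/mL that is 225 mg per 24 h if volumes are totals. Over one four-hour interval, bolus only, it is 4 × 10 = 40 mL (50 mg) against 10 mL (12.5 mg).

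**Against the quoted experience.** Section 5.1.3 reports total daily doses of up to 400 mg in clinical studies. The four-hourly schedule stays below that on either reading of volume (75–135 or 150–270 mg). The hourly schedule stays below it if volumes are totals (300–360 mg) and exceeds it if they are per catheter (600–720 mg).

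**Sample size.** Section 12.6.2 uses a standard deviation of 20 mg, a difference of 10 mg and 80% power. With a two-sided alpha of 0.05 (assumed, because it is not stated), the t-test gives 63.8, so 64 per arm as planned. The infusion rate does not enter that calculation.

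**The case against.** The strongest reply is that the documents already settle the intended dose. Sections 4.2.1 and 6 are the prescriptive sections, they agree, and one of them forbids changes. Section 5.1.1 is a product description that says the pump will be set to the institution's protocol, so it can be read as deferring to a schedule given elsewhere. Harm would require staff to follow a device section against two explicit dosing sections. There are partial safeguards: the pump can carry time-stamped infusion parameters, and the monitoring committee reviews protocol deviations.

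Most of this stands, and it limits the weight of the point. It does not remove the error. The list in 5.1.1 matches the trial dosing in every other setting, so it reads as the trial's pump program. The safeguards would detect a wrong setting after the event; they would not prevent it.

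A second objection is that per-catheter versus total volume is a separate question. That is fair. There is even a weak hint towards totals: the pump is for single-patient use, and Section 5.3 offers up to 200 units for 128 patients, whereas two each would need 2 × 128 = 256. This is inference, not a statement in the protocol, so the question remains a request for clarification.

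Finally, the 400 mg figure is reported experience rather than a limit, and Section 5.1.3 says the maximum must be individualised. Falling below or above it therefore proves neither safety nor harm.

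**Conclusion.** The inconsistency is real, and the 5.1.1 line is wrong as written. Measured against 4.2.1 and 6, it gives 4.0 times the bolus volume and 4.0 to 2.7 times the total daily infusion as the basal rate goes from 0 to 2 mL/h. The ratios hold whether volumes are totals or per catheter. The 225 mg daily excess assumes totals; per catheter it would be 2 × 225 = 450 mg.

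The four-hourly interval is very probably the intended one, because both dosing sections and the intra-operative line of the same list use it. No document indicates that any patient received or will receive hourly boluses. The point should be fixed because it concerns how a drug is delivered; it does not undermine the trial's design, sample size or planned analysis.

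**What to change.** - Have the clinical team confirm the four-hourly interval. Then amend the post-operative line in 5.1.1 to a 10 mL auto-bolus every four hours, keeping the optional basal rate of 1 or 2 mL/h.
- Check the pump programs against the corrected line.
- As a separate clarification, add a phrase to 4.2.1 and 6 saying whether each volume is per catheter or the total across both.

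The cost is one corrected line, one check of the pump programs and one added phrase in each of two sections. The sample size and planned analysis do not change.
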